Appendix 3. Examples of Coadministered Drugs that Need Additional Consideration

Strong Inhibitors of CYP3A	Moderate Inhibitors of CYP3A
boceprevir	aprepitant
clarithromycin ^a	cimetidine
cobicistat ^a	ciprofloxacin
conivaptan ^a	clotrimazole
danoprevir and ritonavir ^b	crizotinib,
diltiazem ^a	cyclosporine
elvitegravir and ritonavir ^b	dronedarone ^a
grapefruit juice	erythromycin
idelalisib	fluconazole
indinavir and ritonavir ^b	fluvoxamine
itraconazole ^a	imatinib
ketoconazole,	tofisopam
lopinavir and ritonavir ^{a,b}	verapamil ^a
nefazodone	
nelfinavir ^a	
paritaprevir and ritonavir and (ombitasvir and/or dasabuvir) ^b	
posaconazole	
ritonavir ^{a, b}	
saquinavir and ritonavir ^{a, b}	
telaprevir ^a	
tipranavir and ritonavir ^{a, b}	
troleandomycin	
voriconazole	

Note: After discontinuation of the strong or moderate CYP3A inhibitor, wait 3 days before resuming ACP-319 or acalabrutinib.

- a. Inhibitor of P-glycoprotein.
- b. Ritonavir is usually given in combination with other anti-HIV or anti-HCV drugs in clinical practice. Caution should be used when extrapolating the observed effect of ritonavir alone to the effect of combination regimens on CYP3A activities.

Strong Inducers of CYP3A	Moderate Inducers of CYP3A
carbamazepine	bosentan
enzalutamide	efavirenz
mitotane	etravirine
phenytoin	modafinil
rifampin	
St. John's wort ^a	

- a. The effect of St. John's wort varies widely and is preparation-dependent.

P-gp Inhibitors	BCRP Inhibitors	Narrow Therapeutic Index P-gp Substrates
amiodarone	curcumin	digoxin
carvedilol	cyclosporine A	everolimus
clarithromycin	eltrombopag	sirolimus
dronedarone		
itraconazole		
lapatinib		
lopinavir and ritonavir		
propafenone		
quinidine		
ranolazine		
ritonavir		
saquinavir and ritonavir		
telaprevir		
tipranavir and ritonavir		
verapamil		

Source: FDA Drug Development and Drug Interactions: Table of Substrates, Inhibitors and Inducers. Web link Accessed 18 July 2018:
<http://www.fda.gov/Drugs/DevelopmentApprovalProcess/DevelopmentResources/DrugInteractionsLabeling/ucm093664.htm#inVivo>

Bile-Acid Sequestrants	Proton-Pump Inhibitors	H2-Receptor Antagonists
cholestyramine	dexlansoprazole	cimetidine
colestipol	esomeprazole	famotidine
colesevelam	lansoprazole	nizatidine
	omeprazole	ranitidine
	rabeprazole	
	pantoprazole	

Source: FDA Established Pharmacologic Class Text Phrase. Web link accessed 18 July 2018:
<https://www.fda.gov/downloads/drugs/guidancecomplianceregulatoryinformation/lawsactsandrules/ucm428333.pdf>

Appendix 4. Performance Status Scores

Grade	ECOG
0	Fully active, able to carry on all pre-disease performance without restriction
1	Restricted in physically strenuous activity but ambulatory and able to carry out work of a light or sedentary nature, e.g., light house work, office work
2	Ambulatory and capable of all self-care but unable to carry out any work activities. Up and about more than 50% of waking hours
3	Capable of only limited self-care, confined to bed or chair more than 50% of waking hours
4	Completely disabled. Cannot carry on any self-care. Totally confined to bed or chair
5	Dead

As published in Am J Clin Oncol:

Credit: Eastern Cooperative Oncology Group Chair: [name]

Available at: http://www.ecog.org/general/perf_stat.html. Accessed 23 August 2013.

CCI

CCI

CCI

Appendix 6. Adverse Event Assessment of Causality

Is there a reasonable possibility that the event may have been caused by study drug?

No ___ Yes ___

The descriptions provided below will help guide the principal investigator in making the decision to choose either “yes” or “no”:

No = There is no reasonable possibility that the event may have been caused by study drug.

The adverse event:

- may be judged to be due to extraneous causes such as disease or environment or toxic factors
- may be judged to be due to the subject’s clinical state or other therapy being administered
- is not biologically plausible
- does not reappear or worsen when study drug is re-administered
- does not follow a temporal sequence from administration of study drug

Yes = There is a reasonable possibility that the event may have been caused by study drug.

The adverse event:

- follows a temporal sequence from administration of study drug
- is a known response to the study drug based on clinical or preclinical data
- could not be explained by the known characteristics of the subject’s clinical state, environmental or toxic factors, or other therapy administered to the subject
- disappears or decreases upon cessation or reduction of dose of study drug
- reappears or worsens when study drug is re-administered

Appendix 7. Actions Required in Cases of Increases in Liver Biochemistry and Evaluation of Hy's Law

INTRODUCTION

This Appendix describes the process to be followed to identify and appropriately report potential Hy's law (PHL) cases and Hy's law (HL) cases. It is not intended to be a comprehensive guide to the management of elevated liver biochemistries.

During the course of the study, the investigator will remain vigilant for increases in liver biochemistry. The investigator is responsible for determining whether a subject meets PHL criteria at any point during the study. All sources of laboratory data are appropriate for the determination of PHL and HL events; this includes samples taken at scheduled study visits and other visits, including central and all local laboratory evaluations, even if collected outside of the study visits (e.g., PHL criteria could be met by an elevated ALT from a central laboratory and/or elevated total bilirubin from a local laboratory). The investigator will also review adverse event (AE) data (e.g., for AEs that may indicate elevations in liver biochemistry) for possible PHL events.

The investigator participates with the sponsor in the review and assessment of cases meeting PHL criteria to agree whether HL criteria are met. HL criteria are met if there is no alternative explanation for the elevations in liver biochemistry other than drug-induced liver injury (DILI) caused by the investigational medicinal product (IMP). The investigator is responsible for recording data pertaining to PHL/HL cases and for reporting AEs and SAEs according to the outcome of the review and assessment in line with standard safety-reporting processes.

DEFINITIONS

Potential Hy's Law

AST or ALT ≥ 3 x ULN together with total bilirubin ≥ 2 x ULN at any point during the study after the start of study drug, irrespective of an increase in alkaline phosphatase.

Hy's Law

AST or ALT ≥ 3 x ULN together with total bilirubin ≥ 2 x ULN, where no reason other than the IMP can be found to explain the combination of increases (e.g., elevated alkaline phosphatase indicating cholestasis, viral hepatitis, or another drug).

For PHL and HL, the elevation in transaminases must precede or be coincident with (i.e., on the same day) the elevation in total bilirubin, but there is no specified timeframe within which the elevations in transaminases and total bilirubin must occur.

IDENTIFICATION OF POTENTIAL HY'S LAW CASES

Laboratory data must be comprehensively reviewed by the investigator for each subject to identify laboratory values meeting the following criteria:

- *ALT $\geq 3 \times$ ULN*
- *AST $\geq 3 \times$ ULN*
- *Total bilirubin $\geq 2 \times$ ULN*

When the identification criteria are met from central or local laboratory results, the investigator will perform the following:

- *Notify the sponsor representative/Medical Monitor by telephone and report the PHL case as an SAE of Potential Hy's law: seriousness criteria "Important medical event" and causality assessment "yes/related" or in accordance with the clinical study protocol as appropriate.*
- *Request a repeat of the test (new blood draw) without delay*
- *Complete the appropriate unscheduled laboratory electronic Case Report Form (eCRF) module(s)*
- *Perform follow-up on subsequent laboratory results according to the guidance provided in the clinical study protocol, as applicable*

REVIEW AND ASSESSMENT OF POTENTIAL HY'S LAW CASES

The instructions in this section should be followed by the investigator for all cases where PHL criteria are met.

As soon as possible after the biochemistry abnormality is initially detected, the study Medical Monitor and the Investigator will review available data, to agree whether there is an alternative explanation for meeting PHL criteria other than DILI caused by the IMP and to ensure that timely analysis and reporting to health authorities within 15 calendar days from the date PHL criteria were met.

Where there is an agreed alternative explanation for the ALT or AST and total bilirubin elevations, a determination of whether the alternative explanation is an AE will be made and, subsequently, whether the AE meets the criteria for an SAE:

- *If the alternative explanation is **not** an AE, record the alternative explanation on the appropriate eCRF.*

- *If the alternative explanation is an AE/SAE, update the previously submitted PHL SAE accordingly with the new information (reassessing event term, causality, and seriousness criteria) following the sponsor's standard processes.*

*If it is agreed that there is **no** explanation that would explain the ALT or AST and total bilirubin elevations other than the IMP, then:*

- *Send updated SAE (report term "Hy's law") according to the sponsor's standard processes:*
 - *The "Medically Important" serious criterion should be used if no other serious criteria apply.*
 - *Because there is no alternative explanation for the HL case, a causality assessment of "related" should be assigned.*

If there is an unavoidable delay of over 15 calendar days in obtaining the information necessary to assess whether the case meets the criteria for HL, then it is assumed that there is no alternative explanation until an informed decision can be made:

- *Provide any further update to the previously submitted SAE of PHL (report term now "Hy's law case"), ensuring causality assessment is related to IMP and seriousness criteria are medically important, according to clinical study protocol process.*
- *Continue follow-up and review according to the agreed plan. After the necessary supplementary information is obtained, repeat the review and assessment to determine whether HL criteria are still met. Update the previously submitted PHL SAE report following the clinical study protocol process, according to the outcome of the review.*

ACTIONS REQUIRED FOR REPEAT EPISODES OF POTENTIAL HY'S LAW

This section is applicable when a subject meets PHL criteria while receiving study treatment and has already met PHL criteria at a previous on-study treatment visit. The requirement to conduct follow-up, review, and assessment of a repeat occurrence(s) of PHL is based on the nature of the alternative cause identified for the previous occurrence.

The investigator should determine the cause for the previous occurrence of PHL and answer the following question:

Was the alternative cause for the previous occurrence of PHL determined to be the disease under study (e.g., chronic or progressing malignant disease, severe infection, or liver disease)?

- If the answer is No:

Follow the process described in “Potential Hy’s Law Criteria Met” in this Appendix for reporting PHL as an SAE.

- If the answer is Yes:

Determine whether there has been a significant change in the subject’s condition compared with the previous occurrence of PHL. Note: A “significant” change in the subject’s condition refers to a clinically relevant change in any of the individual liver biochemistry parameters (ALT, AST, or total bilirubin) in isolation or in combination or a clinically relevant change in associated symptoms. The determination of whether there has been a significant change will be at the discretion of the investigator; this may be in consultation with the study medical monitor if there is any uncertainty.

- If there is no significant change, no action is required.
- If there is a significant change, follow the process described in “Potential Hy’s Law Criteria Met” in this Appendix for reporting PHL as an SAE.

LABORATORY TESTS

The list below represents a comprehensive list of follow-up tests that may aid in assessing PHL/HL.

Test results used to assess PHL/HL should be recorded on the appropriate eCRF.

Additional standard chemistry and coagulation tests	GGT LDH Prothrombin time INR
Viral hepatitis	IgM anti-HAV IgM and IgG anti-HBc HBsAg HBV DNA IgM and IgG anti-HCV HCV RNA IgM anti-HEV HEV RNA
Other viral infections	IgM & IgG anti-CMV IgM & IgG anti-HSV IgM & IgG anti-EBV
Alcoholic hepatitis	Carbohydrate deficient transferrin (CD-transferrin)
Autoimmune hepatitis	Antinuclear antibody (ANA) Anti-Liver/Kidney Microsomal Ab (Anti-LKM) Anti-Smooth Muscle Ab (ASMA)
Metabolic diseases	alpha-1-antitrypsin Ceruloplasmin Iron

Ferritin
Transferrin
Transferrin saturation

Reference

## TABLE OF ABBREVIATIONS

ACP-196	Acalabrutinib (acalabrutinib = ACP-196)
AE	adverse event
BID	twice per day (dosing)
BMI	body mass index
CCNU	lomustine
CI	confidence interval
CR	complete response (remission)
CRF	case report form
CSR	clinical study report
CTCAE	Common Terminology Criteria for Adverse Events
DOR	duration of response
ECOG	Eastern Cooperative Oncology Group
ECI	Events of Clinical Interest
EIAEDs	enzyme-inducing antiepileptic drugs
FACT-Br	Functional Assessment of Cancer Therapy – Brain
FDA	Food and Drug Administration
GBM	Glioblastoma Multiform
ICF	Informed Consent Form
IPD	Important Protocol Deviation
K-M	Kaplan-Meier
MDSCs	myeloid-derived suppressor cells
MedDRA	Medical Dictionary for Regulatory Activities
mmHG	millimeter of mercury
NCI	National Cancer Institute
ORR	overall response rate
OS	overall survival
PD	pharmacodynamic, pharmacodynamics, or progressive disease
PFS	progression-free survival
PFS-4	4-month progression-free survival
PFS-6	6-month progression-free survival
PK	pharmacokinetic or pharmacokinetics
PO	orally
PR	partial response (remission)
PRO	patient-reported outcome
PT	preferred terms
QD	once per day (dosing)
RANO	Response Assessment in Neuro-oncology (criteria)
RCI	Reliable Change Index (methodology)
SAC	Scientific Advisory Committee
SAE	serious adverse event
SAP	statistical analysis plan
SD	stable disease

SI	International System of Units
SMQ	Standardized MedDRA Queries
SOC	system organ class
SRC	Safety Review Committee
TEAEs	treatment emergent adverse events
TESAEs	treatment-emergent serious adverse events
WHO	World Health Organization
WHODRUG	World Health Organization Drug Dictionary

## **1 INTRODUCTION**

The purpose of this statistical analysis plan (SAP) is to provide details of the statistical analyses that have been outlined within the protocol Amendment 2.0, 21 March 2017 for [REDACTED] ACE-ST-209 (Glioblastoma multiforme, GBM). The scope of this plan includes the final analysis that are planned and will be executed by the Biometrics department or designee. Any changes to the methods described in the final SAP will be documented in the clinical study report (CSR).

## **2 OBJECTIVES**

### **2.1 Primary Objectives**

- To characterize the safety profile of acalabrutinib monotherapy in subjects with recurrent GBM
- To evaluate the efficacy of acalabrutinib monotherapy in subjects with recurrent GBM based on overall response rate (ORR) per the Response Assessment in Neuro-oncology (RANO) criteria

### **2.2 Secondary Objectives**

- To evaluate the efficacy of acalabrutinib monotherapy based on duration of response (DOR) per RANO criteria
- To evaluate the efficacy of acalabrutinib monotherapy based on progression-free survival (PFS) per RANO criteria
- To evaluate the efficacy of acalabrutinib monotherapy based on 6-month PFS (PFS-6) rate per RANO criteria
- To evaluate the efficacy of acalabrutinib monotherapy based on overall survival (OS)

### **2.3 Exploratory Objectives**

[REDACTED]

## **3 STUDY OVERVIEW**

### **3.1 Study Design**

This Phase 1b/2, multicenter, open-label study was designed to evaluate the efficacy and safety of acalabrutinib in subjects with recurrent GBM who had progressed after 1 or

2 prior systemic treatment regimens. Subjects meeting the eligibility criteria for the study were assigned 1:1 to one of the following cohorts:

Cohort 1: acalabrutinib 200 mg administered PO BID

Cohort 2: acalabrutinib 400 mg administered PO QD

Under original protocol, an interim analysis was scheduled after the 12th subject was enrolled in each arm (n=24). If acceptable safety and efficacy (e.g., 2 or more of the 12 subjects [ $\geq 16.7\%$ ] achieve a complete response [CR] or partial response [PR]; additional criteria may be considered by the SAC) are observed in either cohort, the sponsor may choose to expand the study to a total of 72 subjects. The acalabrutinib dosage for the Phase 2 portion of the study will be based on available safety and efficacy data from the Phase 1b cohorts. However, due to the paucity of EIAED-treated subjects, an interim analysis was held after 16 non-EIAED subjects and 1 subject on EIAED were enrolled in the study. The first interim analysis did not raise any safety concerns and showed some response in the 200 mg BID group, while no response in 400 mg QD group. Therefore, the SAC recommended discontinuing Cohort 2 (400 mg QD) and enrolling 7 additional non-EIAED subjects planned for Phase 1b of the study into Cohort 1 (200 mg BID). Under amendment 2 of the protocol, a second interim analysis for safety and efficacy was performed after enrolling an additional 7 subjects, once 15 total subjects enrolled in the 200 mg BID cohort (8 subjects enrolled prior to first interim analysis, and an additional 7 subjects planned to complete Phase 1b).

Under amendment 2 of the protocol, the efficacy criteria for success for phase 1b was as follows: an ORR rate of 3/15 (20%) with a lower bound of a 1-sided 90% exact binomial confidence interval of 7.1% would warrant a recommendation to expand study to phase 2 an enroll additional 28 subjects. Using these criteria, a lower bound of confidence interval of 7.1% would be greater than 5% (ORR estimate for the standard of care CCNU). Based on these criteria, the SAC and the Safety Review Committee did not recommend continuing the study (initiating Phase 2) after reviewing the results of the 2nd interim analysis.

Refer to Amendment 2.0 section 3.0 for more details.

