Treatment can continue until the end of trial, defined as 52 weeks after the last subject is enrolled to the study, for subjects without disease progression and who are tolerating therapy. Subjects who have **confirmed** progressive disease or who start new anticancer therapy for GBM will discontinue study treatment.

[figure not shown]
Subjects who are *still on treatment at the end of the study* and deriving clinical benefit from acalabrutinib treatment may continue treatment. *At the time of the final data cutoff (DCO) and database closure, subjects who remain in this study may be transitioned to a separate rollover study or remain within this study for continued access to study drug. Once all active subjects are eligible to continue to receive acalabrutinib and after database closure, this study would be considered closed. There will be no further data collection other than reporting of SAEs per [Section 6.2](#). Access within this study will enable continued treatment with visit assessments per standard of care, whereas the separate rollover study will enable treatment continuation with visit assessments and data collection per the rollover study protocol.*

Refer to [Appendix 1](#) for a comprehensive list of study assessments and their timing. The study schema is provided below ([Figure 3-1](#)).

Note: Under Amendment 2 of the protocol, an interim analysis was scheduled after the 12th subject was enrolled in each arm (n=24). However, due to the paucity of EIAED-treated subjects, an interim analysis was held after 16 non-EIAED subjects and 1 subject on EIAED were enrolled in the study. The first interim analysis did not raise any safety concerns and showed some response in the 200 mg-BID group, while no response in 400-mg QD group. Therefore, the SAC recommended discontinuing Cohort 2 (400 mg QD) and enrolling 7 additional non-EIAED subjects planned for Phase 1b of the study into Cohort 1 (200 mg BID). A second interim analysis for safety and efficacy will be performed after enrolling an additional 7 subjects, once 15 total subjects enrolled in the 200-mg BID cohort (8 subjects enrolled prior to first interim analysis, and an additional 7 subjects planned to complete Phase 1b). An ORR rate of 3/15 (20%) will yield a lower bound of a 1-sided 90% exact binomial CI of 7.1%, which is greater than 5% (ORR estimate for the standard of care CCNU). Based on these

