### **3.2 Sample Size**

The sample size for the overall study included subjects enrolled in Phase 1b and Phase 2 treated with the same dose regimen. An ORR observed in standard of care for second-line therapies (CCNU) ranged around 5 to 10%. While bevacizumab (Avastin)

demonstrated an ORR > 20%, considerable toxicities were reported. To reject the null hypothesis of ORR ≤ 5% in favor of an alternative hypothesis that the ORR is ≥ 20%, 43 subjects will preserve approximately 88% power to detect the difference at a 0.025 significance level by a 1-sided exact test.

However, the initiation of part 2 of the study was dependent on the results of part 1b. The sample size for part 1b was chosen empirically to be 24 subjects. Furthermore, the sample size for subjects treated with acalabrutinib dose of 200mg BID was 15, while 9 subjects were treated with acalabrutinib dose of 400 mg. The sample size and design changes for part 1b are summarized in the table below:

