### **10.7.1 Best Overall Response, Disease Control Rate and Overall Response Rate per RANO criteria**

Measurable disease (bidimensional) as defined by the RANO criteria. RANO criteria (Wen 2010) will be followed for selection of measurable and non-measurable lesions and about the number of lesions to be assessed, as well as for the assessments of response and progression.

Disease Control Rate (DCR) is defined as the proportion of subjects who achieve a best response of SD, PR or CR at any point of the study.

Overall response Rate (ORR) is defined as the proportion of subjects who achieve a best response of PR or CR at any point of the study.

The primary analysis of DCR and ORR will be conducted using safety analysis set. DCR and ORR will be calculated with the corresponding exact binomial 2-sided 95% CI and 1-sided 90% CI (or 2-sided 80% CI) for treatment cohort.

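### The exact one-sided 90% lower bound for 3 responders of 15 is 7.6%, not the 7.1% stated in the Phase 1b success criterion; the decision rule is unaffected

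*SAP*

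**What the plan says.** Protocol section 3.0 sets out the basis for the second interim analysis in the 200 mg BID cohort: "An ORR rate of 3/15 (20%) will yield a lower bound of a 1-sided 90% exact binomial CI of 7.1" percent, which it notes is above the 5% response rate taken for lomustine (CCNU). The protocol synopsis repeats this.

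SAP 3.1 presents the same numbers as the efficacy criterion for expanding to Phase 2, "an ORR rate of 3/15 (20%) with a lower bound of a 1-sided 90% exact binomial confidence interval of 7.1" percent, and adds that "a lower bound of confidence interval of 7.1% would be greater than 5% (ORR estimate for the standard of care CCNU"). It then reports that the two committees did not recommend opening Phase 2.

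The denominator is stated consistently. SAP 3.1 places the analysis "once 15 total subjects enrolled in the 200 mg BID cohort (8 subjects enrolled prior to first interim analysis" plus 7 more), and SAP 3.2 says "the sample size for subjects treated with acalabrutinib dose of 200mg BID was 15".

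For the final analysis, SAP 10.7.1 plans the response rate with the "exact binomial 2-sided 95% CI and 1-sided 90% CI (or 2-sided 80% CI"), which is the same type of interval as in the criterion.

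**The concern.** The text fixes every input to the bound: the responder count, the number of subjects, the confidence level, the sidedness and the exact method. Only one value can follow, and it is not 7.1%.

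What is at stake is the accuracy of the record rather than a decision. The figure is the only statement of precision attached to the Phase 1b go/no-go criterion, and SAP 3.1 says the committees' recommendation rested on that criterion. A programmer or a reader of the study report who applies the interval in SAP 10.7.1 to 3/15 will get 7.6% and meet an unexplained discrepancy.

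**Working it through.** **Inputs**
- x = 3 responders, n = 15 subjects (Protocol synopsis and 3.0; SAP 3.1). The denominator is 8 + 7 = 15, and 15 + 28 = 43 matches the planned Phase 2 total.
- Exact binomial, one-sided, 90%, so the tail area is 0.10 (same places). SAP 10.7.1 treats this as equivalent to a two-sided 80% interval.
- Reference response rate: 5% (Protocol 3.0; SAP 3.1).

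**Formula.** The exact (Clopper-Pearson) lower bound is the value p_L that solves

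P(X ≥ x | n, p_L) = 0.10,

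or equivalently the 0.10 quantile of a Beta(x, n − x + 1) distribution. For x = 3 and n = 15,

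P(X ≥ 3) = 1 − (1 − p)^15 − 15·p·(1 − p)^14 − 105·p²·(1 − p)^13.

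**Test of the stated figure, p = 0.071**

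1 − 0.3313 − 0.3798 − 0.2032 = 0.0857.

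The tail is 8.57%, not 10%, so for 3/15 the value 7.1% is a 100 − 8.57 = 91.4% one-sided bound. Rounding does not explain the gap: p = 0.0705 gives 0.0843 and p = 0.0715 gives 0.0871.

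**Correct value.** The 0.10 quantile of Beta(3, 13) is 0.07586. Check at p = 0.07586:

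1 − 0.3062 − 0.3771 − 0.2167 = 0.1000.

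The bound is 7.59%, or 7.6% rounded. The discrepancy is 7.59 − 7.1 = 0.49, about 0.5 percentage points.

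**Could another method give 7.1% for 3/15?**

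| Method | Lower bound |
|---|---|
| Exact, one-sided 95% | 5.7% |
| Exact, one-sided 97.5% | 4.3% |
| Wald, one-sided 90% | 6.8% |
| Wald with continuity correction | 3.4% |
| Wilson | 10.1% |
| Wilson with continuity correction | 7.8% |
| Agresti-Coull | 9.7% |
| Jeffreys | 9.8% |
| Mid-P | 9.3% |
| Logit | 9.9% |
| Arcsine | 8.6% |
| Blaker, two-sided 80% | 10.3% |
| Sterne, two-sided 80% | 10.4% |

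None does, and a non-exact method or another level would contradict the label in the text. The same exact formula gives 7.10% for 3/16, so a denominator slip is possible, but neither document says how 7.1% was obtained.

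**Effect on the decision rule** (exact one-sided 90% lower bounds)

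| Responders of 15 | Lower bound | Above 5%? |
|---|---|---|
| 2 | 3.6% | No |
| 3 | 7.6% | Yes |
| 4 | 12.2% | Yes |

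The smallest qualifying count is 3. If 7.1% is instead read literally as the threshold, 3/15 (7.6%) still passes and 2/15 still fails. As a direct check against the reference rate, P(X ≥ 3 | p = 0.05) = 1 − 0.46329 − 0.36576 − 0.13475 = 0.0362, below 0.10.

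**The case against.** The best defence is that the slip changes nothing. The comparison that matters is with 5%, and 3/15 passes and 2/15 fails on either figure. The second interim analysis has been done and Phase 2 was not recommended. The SAP tests no hypothesis (section 5), and section 10.7.1 computes intervals from the observed counts, so 7.1% is not an input to any output. The repeated appearances are one figure carried forward. Amending two documents for a decision already taken would be out of proportion.

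Most of this stands. It settles how important the error is and supports handling it in the study report. It does not make the number right: nothing else in either document corrects it, and it sits inside what the SAP calls the success criterion.

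Two further cautions are fair. The link to 3/16 is an inference from arithmetic only; the 16 in the documents counts non-EIAED subjects across both cohorts at the first interim analysis, not the 200 mg BID denominator. And the documents give 3/15 as the criterion without writing a rule of at least 3 of 15. That rule is the natural reading and follows from the bounds, but spelling it out is a clarification, not part of the numerical correction.

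**Conclusion.** The stated bound is wrong as labelled: 7.6% (7.59%) should stand in place of 7.1%, a difference of 0.5 percentage points. The conclusion assumes that an exact binomial interval means Clopper-Pearson, which the documents do not name but which is the standard reading; none of the other methods tried yields 7.1%. The error understates the bound, so it is on the conservative side. It leaves the 5% comparison, the count of 3 of 15, the sample size, the planned analyses and the decision not to open Phase 2 unchanged. This is a minor correction.

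**What to change.** Replace 7.1% with 7.6% in the protocol synopsis, in Protocol 3.0 and in both places in SAP 3.1. Since Phase 1b is complete, one sentence in the clinical study report would also suffice; SAP section 1 already uses that report to document changes to its methods. If the figure came from a different method or denominator, state which.

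An optional clarification is to write the criterion as at least 3 responders of 15, with an exact one-sided 90% lower bound of 7.6% against 5%, noting that 2/15 gives 3.6%.

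The cost is a text correction or a single sentence. No rule, sample size or analysis changes.
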